- Mean NK cell density in tumor tissue from harvested prostate glands of patients

- Proportion of treated patients with detectable Enoblituzumab in prostate tumor specimens(fresh frozen section)
- Proportion of pathological complete responses (pCR) in each treatment group
- Proportion of patients achieving a PSA response rate (PSA <0.1 ng/mL) at 3 months after prostatectomy
- Median time-to-PSA-recurrence (PSA ≥0.2 ng/mL) after radical prostatectomy
- Median PSA decrease prior to radical prostatectomy
- To assess Gleason grade change post neoadjuvant Enoblituzumab treatment, by comparing prostatectomy Gleason sum to pre-treatment biopsy Gleason sum

Statistical Our primary objective(s) is to characterize safety, tolerability, and feasibility of treatment of men with Enoblituzumab in the neoadjyuant setting as well as obtain an methods estimate of PSA₀ response rate 12 months following radical prostatectomy. The trial will monitor toxicity and safety, as well as feasibility with respect to its impact on subsequent surgery. The secondary objective will be to evaluate an anti-tumor effect consistent with the agent's proposed mechanism of action (MOA), antibody-dependent cellular cytotoxicity (ADCC). Tumor cell death will be quantified by Caspase staining, and post-treatment apoptotic index compared with that from the pre-treatment biopsy. Sample size is driven by detecting a pharmacodynamic effect of the agent based on the key secondary endpoint of tumor cell death as well as in the expansion cohort to obtain an estimate of PSA_0 response. A biologically meaningful treatment effect will be deemed to be one where the tumor cell apoptosis is two-fold higher after Enoblituzumab therapy. Previous study showed that baseline apoptosis, measured by Caspase staining, is 0.06 +/- 0.08 (Mean +/-SD) for Gleason 4 and 0.2 ± 0.2 for Gleason 3 (Kim et al 2016). Based on this data, we assume that the coefficient of variation of tumor cell death measure is 1.2 and the correlations between the measures pre- and post-treatment is moderate at 0.4, 16 subjects will provide 88% power to detect a 2-fold increase in apoptotic tumor cells after the treatment compared to baseline, using a one-sided paired t-test with significance level 0.05. Other endpoints will be exploratory in nature, and quantified using descriptive statistics.

For the expansion cohort (amendment 1):

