10. STATISTICAL CONSIDERATIONS

10.1 Study Design and Sample Size

This is a single-center, single arm, open-label phase II study evaluating the safety, anti-tumor effect, and immunogenicity of neoadjuvant MGA271 given weekly for 6 doses beginning 50 days prior to radical prostatectomy in men with high-risk localized prostate cancer. Our primary objective is to characterize safety, tolerability, and feasibility of treatment of men with Enoblituzumab in the neoadjvuant setting. The trial will monitor toxicity and safety, as well as surgery related adverse events. (see Section 10.2.1). The secondary objective will be to evaluate immune response consistent with the agent's proposed mechanism of action (MOA), antibody-dependent cellular cytotoxicity (ADCC). Tumor cell death will be quantified by Caspase 3 staining, and post-treatment apoptotic index compared with that from the pre-treatment biopsy. The sample size is driven by detecting a pharmacodynamic effect of the agent based on the key secondary endpoint of tumor cell death. A biologically meaningful treatment effect will be deemed to be one where the tumor cell apoptosis is two-fold higher after MGA271 therapy. Previous study showed that baseline apoptosis, measured by Caspase staining, is 0.06 + - 0.08 (Mean + - SD) for Gleason 4 and 0.2 ± 0.2 for Gleason 3 (Kim et al. 2016). Based on this data, we assume that the coefficient of variation of tumor cell death measure is 1.2 and the correlations between the measures pre- and post-treatment is moderate at 0.4, 16 subjects will provide 88% power to detect a 2-fold increase in apoptotic tumor cells after the treatment compared to baseline, using a one-sided paired t-test with significance level 0.05.

In Amendment 1, the study was expended to enroll an additional 16 patients for a total of 32 patients to continue evaluating safety and better estimate the clinical benefit of Enoblituzumab in terms of undetectable PSA level (<0.1 ng/mL) at 12 months following radical prostatectomy.

Patients will be replaced if they are removed from the study after signing the informed consent but before undergoing radical prostatectomy. Patients receiving at least one dose of the study drug will be included in both safety and efficacy analyses.

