10.2 Study Endpoints

10.2.1 Analysis of the primary endpoints

Safety and feasibility

Frequency of adverse events will be described using summary statistics. The proportion of patients with an adverse event will be reported with an exact binomial 95% confidence interval. All subjects receiving at least one dose of the study drug(s) will be evaluable for toxicity.

Early stopping rules for toxicity: Toxicity will be monitored closely and continuously. Any grade-3/4 local reactions (erythema, swelling, pain) attributable to MGA271 or Grade 3 infusion-related reaction or cytokine release syndrome that lasts ≥ 12 hours will be considered AEs for purposes of this stopping rule. A grade 4 infusion related reaction of any duration will be considered AEs for purposes of this stopping rule. If the risk of these adverse events appears to be higher than 33%, we will temporarily halt the study pending dose modification. Specifically, we apply a Bayesian toxicity monitoring rule that suspends the enrollment if the posterior probability of risk being larger than 0.33 is 65% or higher. The monitoring rule uses beta (1.5, 5.5) as prior distribution. This means that our prior guess at the proportion of toxicity is 21%, and there is 90% probability that this proportion is between 3% and 49%. The decision rule for toxicity stopping is as follows:

Study termination if:	3 AEs	4 AEs	5	6	7	8	9	10	11	12	13
In number of patients between:	3 - 4	5 - 7	8 - 10	11 - 12	13 - 15	16 - 18	19 - 21	22 - 24	25 - 27	28 - 30	31- 32

For example, we will interrupt the accrual if 3 patients have AEs among the first 4 receiving treatment. If 4 or more out of the first 5-7 patients have AEs, we will suspend accrual.

The operating characteristics of the stopping rule are shown below and are based on 5000 simulations:

Risk of AE	0.20	0.25	0.30	0.33	0.40	0.45
% of Time study stops	7.5%	18%	33.7%	46%	54.6%	73.3%
Expected sample size	30.3	28.2	25.3	22.8	21.2	17.3

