Early stopping rule for feasibility: We do not anticipate an increase in the surgical difficulty with the use of neoadjuvant MGA271. Men who have had acute (post-biopsy) and prolonged issues (chronic prostatitis) with prostate infection/inflammation are fairly routine in urologic surgical practice, and we anticipate that the immune infiltrate potentially induced by MGA271 would not pose a substantial increase in surgical difficulties. However, in addition to safety, feasibility will be monitored separately. The feasibility rule for this study will be based on a change in surgical outcomes beyond what may be expected for patients without presurgical interventions and that may be attributable to the study drug. These events would include: (1) average blood loss in excess of 2500 mL, (2) average operative time in excess of 3.5 hours, and (3) average hospital stay in excess of 4 days, (4) systemic symptoms (fevers, rash, myelosuppression) compromising the planned surgery. These values are approximately 2 standard deviations above the average surgical outcomes for men undergoing radical prostatectomy at Johns Hopkins Hospital.

We expect no surgery complication in at least 90% cases. We will monitor this endpoint after every patient. If it becomes apparent that the surgeries are being negatively impacted by the pre-surgical investigational treatments, then the study will be suspended for review. Again, we apply a Bayesian monitoring rule that suspends the enrollment if the posterior probability of complications > 0.10 is 80% or higher. The monitoring rule uses beta (1, 9) as prior distribution, based on the expectation that these treatments will not impact the

feasibility of surgery. Instances where the study would be temporarily suspended are listed below.

Stopping rules:

Not feasible if the observed number of	2	3	4	5	6
surgical complications is:					
In number of patients between:	2 - 6	7 - 14	15 - 22	23 - 30	31 - 32

The operating characteristics of the stopping rule are shown below and are based on 5000 simulations:

Risk of surgical complication	0.025	0.05	0.10	0.15	0.20
% of Time study stops	1.1%	5.9%	29.2%	57.7%	81.4%
Expected sample size	31.7	30.7	26.4	20.9	15.3

10.2.1.1 For expansion Amendment 1

Estimation of PSA₀ Response Rate (Undetectable PSA level <0.1 ng/mL) at 12 months following radical prostatectomy

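### The surgical feasibility events (1)–(3) are worded as averages, but the stopping boundary counts one yes/no complication per patient, so the event wording needs correcting.

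*Combined protocol and SAP*

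**What the plan says.** The feasibility rule is in Section 10.2.1 under the early stopping rule for feasibility. It lists four events. The first two read "These events would include: (1) average blood loss in excess of 2500 mL, (2) average operative time in excess of 3.5 hours"; the third is an average hospital stay above 4 days. The fourth, systemic symptoms that compromise surgery, is the only one that describes an individual man. The list is introduced by a condition: the change must go beyond what is expected without presurgical treatment, and be possibly attributable to the drug. On the limits the plan says: "These values are approximately 2 standard deviations above the average surgical outcomes for men undergoing radical prostatectomy at Johns Hopkins Hospital".

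The same section then describes a per-patient rule. It says "We expect no surgery complication in at least 90% cases" and "We will monitor this endpoint after every patient". The criterion is: "Again, we apply a Bayesian monitoring rule that suspends the enrollment if the posterior probability of complications > 0.10 is 80% or higher". With a beta(1, 9) prior, the table suspends the study at 2, 3, 4, 5 or 6 complications in 2–6, 7–14, 15–22, 23–30 or 31–32 patients. Crossing it leads to suspension for review.

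The Synopsis (Statistical methods) makes this part of what the trial monitors: "as well as feasibility with respect to its impact on subsequent surgery".

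**The concern.** A beta-binomial rule needs a numerator and a denominator in patients. An average gives one answer for the whole group at each look, not a number of men. Events (1)–(3) therefore cannot supply the count the table asks for, and no other section says when one man has had a surgical complication. The toxicity rule in the same section avoids the problem: its events belong to individual patients, and it gives a worked example in patients.

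The literal wording is also the less sensitive one. If the limits lie about 2 SD above the institutional average, the trial's own mean would have to worsen by about 2 SD before an event occurred. A minority of clearly abnormal operations would be averaged away. What it means for the boundary not to be crossed depends on how the three events are read.

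**Working it through.** **Inputs, all from Section 10.2.1:** prior beta(1, 9); suspend if the posterior probability that the risk exceeds 0.10 is at least 0.80; a look after each patient; maximum 32; the printed boundary and operating characteristics.

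**1. The boundary.** With r complications in n patients, one yes/no per man, the posterior is beta(1 + r, 9 + n − r). The boundary is the smallest r with P(risk > 0.10) ≥ 0.80.

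| r / n | P(risk > 0.10) | Suspend? |
|---|---|---|
| 2 / 6 | 0.816 | yes |
| 2 / 7 | 0.789 | no |
| 3 / 14 | 0.807 | yes |
| 3 / 15 | 0.786 | no |
| 4 / 22 | 0.807 | yes |
| 4 / 23 | 0.789 | no |
| 5 / 30 | 0.810 | yes |
| 5 / 31 | 0.794 | no |
| 6 / 31 | 0.900 | yes |

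Every boundary from n = 2 to n = 32 agrees with the printed table.

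**2. The operating characteristics.** These come from an exact recursion over independent per-patient events, checked after each patient against the printed boundary.

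| Risk | Stops, exact | Stops, stated | Expected N, exact | Expected N, stated |
|---|---|---|---|---|
| 0.025 | 1.3% | 1.1% | 31.7 | 31.7 |
| 0.05 | 6.3% | 5.9% | 30.6 | 30.7 |
| 0.10 | 29.4% | 29.2% | 26.3 | 26.4 |
| 0.15 | 59.3% | 57.7% | 20.5 | 20.9 |
| 0.20 | 81.7% | 81.4% | 15.3 | 15.3 |

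All stop rates agree within 2 percentage points. The printed figures therefore describe one yes/no event per man.

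**3. How far the literal wording departs from this.** The documents do not give institutional means or SDs, so these are illustrations on assumed values.

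- Six men at 5.0 h and 26 at 2.5 h: (6 × 5.0 + 26 × 2.5) / 32 = 95 / 32 = 2.97 h. The average is below 3.5 h, so there is no event, yet 6 of 32 meets the boundary (posterior 0.89).
- Number of men at 5.0 h needed to push the 32-man average above 3.5 h: 17, 13 or 9 if the others take 2.0, 2.5 or 3.0 h.
- The reverse can also happen. Blood losses of 4500 and 600 mL in the first two men average (4500 + 600) / 2 = 2550 mL. That is over the limit with only one man above it, and one complication crosses no boundary.
- One normally distributed outcome with the limit at mean + 2 SD: if 10% of men exceed it, the per-patient count stops about 29% of trials, while the running average (from the second man on) ever exceeds it in about 4%. If 20% exceed it, the figures are about 82% and 16%.

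**4. Background events on the per-patient reading.** For a normal outcome the share above mean + 2 SD is 0.02275. For three independent outcomes, the share of men over at least one limit is 1 − (1 − 0.02275)³ = 0.0667. At that risk the printed boundary suspends 12.2% of trials with no drug effect. If the three limits were always exceeded by the same men, the share would be 2.3% and the suspension rate 1.0%. These figures ignore event (4) and the attribution condition.

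**The case against.** The strongest reply is that nobody would run the rule on averages. Section 10.2.1 speaks of cases, looks after each patient, and tabulates complications against patients. Limits about 2 SD above the mean are natural outlier limits for an individual. The prior, table and simulations settle the meaning, and an average cannot even be used with the only boundary given. This stands as evidence of intent. It does not make the written events correct, and it leaves open whether a man over two limits counts once.

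A reader might infer that this rule is the only place where impact on surgery is assessed. The documents do not support that. Section 7.4 has perioperative complications recorded, blood loss and length of stay included, with CTCAE grading and attribution made together with urologists. Section 8.2.1 reports adverse events by number, frequency and grade. Section 10.2.1 adds: "The proportion of patients with an adverse event will be reported with an exact binomial 95% confidence interval". None of these defines the count that the feasibility rule uses, but surgical harm would not go unrecorded.

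The consequence is also limited. Crossing the boundary prompts a review, not automatic termination. Monthly meetings (Section 9.3) and ongoing review by the investigator or medical monitor (Section 11.5) run alongside it. The PSA and apoptosis analyses do not use this count.

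Finally, simply counting every man over a limit would drop the plan's attribution condition and raise false suspensions. That is right, and the fix keeps the condition.

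**Conclusion.** The point holds as an error in the event definition. Events (1)–(3) as worded contradict the boundary and operating characteristics they are meant to feed, and taken literally they cannot be entered in the table. The boundary, prior and operating characteristics are correct for per-patient events and need no change.

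Two stronger readings should be resisted. One is that the plan leaves the choice between averages and individuals open; the rest of the section points clearly to individuals. The other is that the trial is likely to reach the wrong feasibility decision. The contrasts in operating time and blood loss rest on assumed values, and the 29% versus 4% and 82% versus 16% comparisons assume normality. They show the direction and possible size of the discrepancy, not its size in this trial.

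The correction is worth making before the rule is relied on, because feasibility is a primary objective and this rule is what turns surgical impact into a decision to suspend.

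**What to change.** In Section 10.2.1, delete the word average from events (1)–(3) and add a definition along these lines: a patient counts once as a surgical complication if his own blood loss exceeds 2500 mL, his own operative time exceeds 3.5 hours, his own stay exceeds 4 days, or systemic symptoms compromise his operation, provided the event goes beyond what is expected and may be attributable to the study drug. The attribution process in Section 7.4 can serve for that judgement.

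State also that a man whose surgery is cancelled for event (4) stays in the count. Section 10.1 says "Patients will be replaced if they are removed from the study after signing the informed consent but before undergoing radical prostatectomy", and without this sentence a clear feasibility failure could be replaced and lost.

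Confirm from the institutional series that the share of men over at least one limit is below the 10% the rule assumes. By the plan's own table, a 5% background share suspends 5.9% of trials and a 10% share suspends 29.2%. If the share is near 10%, the limits should be raised.

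The cost is three deleted words, about three sentences and one look at existing surgical data. No visits or tests are added, and the table stands. The downside is some suspensions from ordinary variation: between about 1% and 12% under the normal assumptions above if attribution is ignored, and fewer if it is applied. Skewed outcomes could change those figures, which is a further reason for the check.

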10.2.2 Analysis of the secondary and exploratory endpoints

The secondary endpoints of this study have previously been defined (see Section 8.3). The statistical analysis of these endpoints is described below. Data transformation will be performed when they are not normally distributed.

• **Apoptotic markers.** The primary objective of pharmacodynamics effect of this study is to determine the immunologic response consistent with the agent's proposed mechanism of action (MOA), antibody-dependent cellular cytotoxicity (ADCC). Tumor cell death will be quantified by TUNEL staining, Caspase 3 staining, and FcGamma staining and will be expressed as the mean staining percentage in tumor samples. Standard deviations, 95% confidence intervals, and ranges will also be reported where appropriate. Means will be

compared pre-treatment (from pre-treatment biopsies) vs. post-treatment using paired sample test.

- **Proliferation markers.** Ki-67 staining will be expressed as the mean staining percentage in tumor samples. Standard deviations, 95% confidence intervals, and ranges will also be reported where appropriate. Means will be compared pre-treatment vs. post-treatment using paired sample test.
- **CD8**⁺ **T cell infiltration.** Mean CD8⁺ T cell staining percentage in harvested prostate tissues will be reported. The standard deviation, 95% confidence interval, median, and range of values will also be reported where appropriate. Since the CD8⁺ T cell quantity is a ratio variable and the distribution is skewed, the log transformation will be used for the analysis. Tissue microarrays (TMAs) using the highest-grade/largest tumor per patient and sampling it with 100-fold redundancy will be used for CD8⁺ T cell quantification. We expect that 3-50% of the spots per patient will be assigned a carcinoma diagnosis by the study pathologist. Cores with both tumor and normal tissue will be excluded if they contain >10% of the other component. The percent positive staining score for CD8⁺ T cells in the spots classified as tumor will be used to quantify the outcome. The mean will be used to pool multiple spot measurements for each patient.
- **PD-L1+ cell density**. The methods for quantifying and analyzing PD-L1 cell density will be similar to those described for CD8⁺ T cell infiltration. Descriptive statistics and graphical summaries will be provided.
- **Regulatory T cell (T_{reg}) density**. The methods for analyzing T_{reg} infiltration will be similar to those described for CD8⁺ T cell infiltration. Descriptive statistics and graphical summaries will be provided. In addition, the CD8⁺/T_{reg} ratio and the CD4⁺/T_{reg} ratio will be computed, and reported using descriptive statistics.
- **CD4**⁺ **T cell density.** The methods for quantifying and analyzing CD4⁺ T cell infiltration will be similar to those described for CD8⁺ T cell infiltration. Descriptive statistics and graphical summaries will be provided.
- **Mean NK cell density**. The methods for quantifying and analyzing NK cell infiltration will be similar to those described for CD8+ T cell infiltration. Descriptive statistics and graphical summaries will be provided.
- **Tissue androgen concentrations**. Intraprostatic androgen concentrations (*i.e.* testosterone and dihydrotestosterone) will be summarized descriptively.
- **Enoblituzumab (MGA271) drug distribution**. Intraprostatic Enoblituzumab staining concentrations will be summarized descriptively.
- Androgen receptor (AR) quantification. Androgen receptor (AR) staining concentrations will be summarized descriptively.
- **Pathological complete responses (pCR)**. This will be defined as an absence of tumor identification on standard histological analysis of the resected prostate specimens.
- **PSA response rates**. This will be defined as an undetectable PSA (<0.1 ng/mL) at 3 months after prostatectomy. The proportion of patients achieving a PSA response will be reported. .
- **Time to PSA recurrence.** This will be defined as the interval from prostatectomy to the time when the serum PSA is ≥0.2 ng/mL. For subjects who have not yet demonstrated PSA recurrence at the time of censoring, patients will be censored at the date of the last

assessment that shows a lack of PSA recurrence. The median time to PSA recurrence after prostatectomy (*i.e.*, the median PSA-recurrence-free survival) will be estimated with 95% confidence intervals using Kaplan-Meier survival analysis.

• **Gleason grade change** post neoadjuvant Enoblituzumab treatment from pre-treatment biopsy. This will be calculated utilizing the highest Gleason grade from the pre-treatment biopsy and the post-treatment prostatectomy.

10.3 Analysis Populations

10.3.1 Intention-to-treat population

All patients who meet eligibility criteria and receive at least one dose of the study drug will be included in the analysis of the primary and secondary endpoints, even if there are subsequent protocol deviations. However, in cases where prostatectomy is not performed or if adequate surgical tissue is not collected, then determination of the secondary endpoints (apoptosis/proliferation marker analysis, tissue CD8⁺ T cell analysis) will not be possible. Patients will be replaced if they are removed from the study after signing the informed consent but before receiving the study drug.

10.3.2 Safety population

All patients enrolled in the study will be included in the safety analysis population and considered evaluable for toxicity from the time of their first dose of the study drug(s). Patients never receiving any of the study drugs will not be included in this analysis. Demographic and baseline characteristics for the safety population will be summarized by number and percent for categorical data and by descriptive statistics for continuous data.

